## 1           **PROTOCOL SYNOPSIS**

### 1.1           **Trial design**

[figure not shown]
This is an interventional, Phase III, double-blind, randomized, placebo-controlled, parallel-group, multi-site, clinical trial to confirm the efficacy and safety of a single intra-articular injection of RTX-GRT7039 versus placebo in subjects who have moderate to severe pain associated with osteoarthritis of the knee despite receiving continued treatment with optimal standard of care (SoC) or who are unable to receive SoC treatment due to contraindications or intolerability.

Approximately 450 subjects will be randomized to receive a single dose of either RTX-GRT7039 or placebo in a 1:1 ratio, with a safety follow-up duration of 52 weeks. In addition to continued SoC treatment, subjects will receive 1 of the following treatments:

- RTX-GRT7039 400 ng single intra-articular injection.
- Placebo to match RTX-GRT7039 single intra-articular injection.

#### 1.1.1           **Trial Design Chart**

See [Figure 1](#) for an illustration of the trial design.

IA = intra-articular; IMP = investigational medicinal product; V = Visit

Figure 1: Trial design chart

### 1.1.2 Brief description of the sequence and duration of all trial periods

This trial comprises a Screening Period, a double-blind Treatment and Follow-up Period with a single intra-articular investigational medicinal product (IMP) injection, at Day 1 culminating in a Final Visit at Week 52.

Each subject is expected to be in the trial for up to 56 weeks (i.e., the Screening Period of up to 30 days followed by the 52-week Treatment and Follow-up Period).

See Section 1.1.1 for a trial design chart and Section 1.6 for a tabular schedule of events (SoE).

## 1.2 Trial objectives and endpoints/outcomes

Objective	Endpoint/Outcome

Primary
 
Demonstrate the analgesic efficacy of intra-articular RTX-GRT7039 compared with placebo in change from baseline at Week 12.
	
Primary
 
Change from baseline in Western Ontario and McMaster Universities Osteoarthritis Index (WOMAC) pain subscale score in the index knee to the score at Week 12.
 
The WOMAC pain subscale, which consists of 5 questions, will be assessed and reported in the electronic diary (e-diary) once weekly with a 48-hour recall, using an 11-point numeric rating scale (NRS, from 0 = no pain to 10 = pain as bad as you can imagine).
 
Timeframe for the assessment: from baseline (assessment at V2) to V5 (Week 12/Day 84).
 
Estimand
 
The primary comparison of interest is the difference in mean change from baseline in 48-hour WOMAC pain subscale at Week 12 in the index knee using an 11-pt NRS (0-10) between RTX-GRT7039 and placebo, in subjects who initiate treatment, as if substantial changes in background medication or addition of new analgesics were not available.

Key Secondary
 
Demonstrate the analgesic efficacy of intra-articular RTX-GRT7039 compared with placebo in change from baseline at Week 26.
	
Key Secondary
 
Change from baseline in WOMAC pain subscale score in the index knee based on the 11-point (0-10) NRS to the score at Week 26.
 
Estimand
 
The secondary comparison of interest is the difference in mean change from baseline in 48-hour WOMAC pain subscale at Week 26 in the index knee using an 11-pt (0-10) NRS between RTX-GRT7039 and placebo, in subjects who initiate treatment, as if substantial changes in background medication or addition of new analgesics were not available.

Demonstrate the efficacy of intra-articular RTX-GRT7039 on function compared with placebo in change from baseline at Week 12 and at Week 26.
	
Change from baseline in WOMAC physical function subscale score at Week 12 and at Week 26.

Objective	Endpoint/Outcome

Objective	Endpoint/Outcome
Demonstrate the efficacy of intra-articular RTX-GRT7039 compared with placebo in percentages of subjects responding according to OMERACT-OARSI criteria at Week 12 at Week 26, at Week 38, and at Week 52.	Percent of responders according to OMERACT–OARSI criteria after a single injection into the index knee at Week 12, Week 26, Week 38, and Week 52.
Demonstrate the efficacy of intra-articular RTX-GRT7039 compared with placebo in patient global impression of change (PGIC).	PGIC at Week 12, Week 26, Week 38, and Week 52.
Demonstrate the quality of life after treatment with RTX-GRT7039 compared with placebo.	Quality of life – EuroQol-5 Dimension Health Questionnaire 5 Levels (EQ-5D-5L): changes from baseline to Week 12, Week 26, Week 38, and Week 52.
	Quality of life – Short form-36 (SF-36): changes from baseline to Week 12, Week 26, Week 38, and Week 52.
Investigate durability of effect (until recurrence of pain).	Durability of effect is defined as time from an improvement in WOMAC pain subscale to pain recurrence.

**Other data to be collected that are not directly attributed to an endpoint**

*To evaluate subject eligibility and to describe the trial population*

- Demographic and other baseline characteristics: Date of signature on the informed consent form, sex, age, body weight, height, body mass index (BMI), race, ethnic group.
- Relevant prior/concomitant treatments (i.e., non-pharmacologic and pharmacologic) used to treat osteoarthritis and osteoarthritis pain and reasons for discontinuing will be collected. Prior and concomitant medications other than for osteoarthritis will be collected.
- Thorough musculoskeletal history (incl. current and history of osteoarthritis, joint surgeries, fractures, joint injuries) and physical examination (incl. evaluation of joints for swelling, redness, tenderness).
- Imaging data (X-ray and magnetic resonance imaging [MRI]), pregnancy test, and drugs of abuse test.

*To assess the efficacy*

- Patient global assessment (PGA) of osteoarthritis.
- Patient-specific functional scale (PSFS).
- Durability of effect – return of pain.
- WOMAC, PGIC, SF-36, and EQ-5D-5L data at time points not related to the primary and secondary endpoints.

*To assess the safety and tolerability of RTX-GRT7039*

- Vital signs (systolic and diastolic blood pressure, pulse rate, respiratory rate).
- Electrocardiogram (ECG).
- Safety laboratory parameters (hematology, clinical chemistry, clotting, and urinalysis dipstick panel).
- Physical examination findings.
- Assessment of procedural pain related to the IMP injection.

• Imaging data (X-ray and MRI).

To assess the treatment satisfaction

• Treatment Satisfaction Questionnaire for Medication (TSQM) scores.

### 1.3 Trial subjects – the population to be studied

Inclusion criteria are reviewed at the Screening Visit (V1) and at Baseline (i.e., V2 before IMP administration). Subjects will only receive IMP if documentation is available showing that they meet all of these inclusion criteria and none of the exclusion criteria.

#### 1.3.1 Inclusion criteria

1. The subject has given written informed consent to participate.
2. The subjects are  $\geq 18$  years of age at the Screening Visit.
3. The subjects have a BMI  $\leq 40.0$  kg/m^2.
4. The subject is willing to adhere to the restricted use of concomitant treatments (see concomitant treatments in Section 1.4.3).
5. The subject has a diagnosis of osteoarthritis of the knee based on American College of Rheumatology criteria and functional capacity class of I-III. Pain at the index knee must be present for at least 6 months prior to Screening Visit.
6. The subject has a Kellgren-Lawrence (KL) grade of 2-4 in the index knee (based on X-ray performed during Screening Visit, assessed by central readers).
7. There is a documented history indicating that subject has insufficient pain relief with optimal standard of care (SoC), i.e.,
  - a. non-pharmacological treatment, and
  - b. 1 or more courses of oral non-steroidal anti-inflammatory drugs (NSAIDs) prescribed by their physician and
  - c. where appropriate, opioids, intra-articular treatment with corticosteroids, and intra-articular treatment with hyaluronic acidin combination or as monotherapies,  
or subject is unable to take SoC due to contraindication or intolerability to 1 or more of the SoC treatments above.  
Further details on the definition of documented history will be provided in the electronic case report form (eCRF) guidance document.
8. The investigator does not consider that any additional benefit can reasonably be expected from further adjustments to the subject's pain treatment.
9. The subject must have a baseline WOMAC pain subscale score  $\geq 5$  on the 11-point (0-10) NRS for the index knee at Screening (assessment in e-diary at V1) and at baseline (assessment in e-diary at V2).
10. Women of child-bearing potential must have a negative pregnancy test at the Screening Visit and prior to the administration of IMP. They must also agree to practice, at a minimum, acceptable measures of birth control for 90 days following administration of IMP.

11. Male subjects must agree to use barrier contraception (condom) during sexual intercourse with women of child-bearing potential after administration of IMP for 90 days. The male subject is willing to ensure that during this period the female sexual partner is additionally practicing contraception, if of childbearing potential.

### **1.3.2 Exclusion criteria**

A single re-screening is accepted for items 4, 5, 6, and 7.

1. The subject reports a WOMAC pain subscale score of 10 on the 11-point (0-10) NRS at Screening (assessment in e-diary at V1) or at baseline (assessment in e-diary at V2) for the index knee.
2. The subject has a WOMAC pain subscale score of  $\geq 4$  on the 11-point (0-10) NRS in the non-index knee at Screening.
3. The subject has past joint replacement surgery of the index knee.
4. The subject had an intra-articular injection of either corticosteroid or intra-articular viscosupplementation (i.e., hyaluronic acid) into the index knee within 90 days of screening.
5. The subject had an injection of platelet-rich plasma or stem cells into the index knee within 6 months of screening.
6. The subject applied topical capsaicin on the index knee within 3 months of Screening.
7. The subject has a history of significant trauma or surgery (e.g., open or arthroscopic) to the index knee within 12 months of Screening.
8. The subject has any known active infection of the index joint, including suspicion of intra-articular infection, ulcer, or open wound anywhere on the index knee.
9. The subject has periarticular pain from any cause other than osteoarthritis, including referred pain, bursitis, or tendonitis.
10. The subject has ipsilateral clinical hip osteoarthritis on the side of the index knee.
11. The subject has pre-existing osteonecrosis, subchondral insufficiency fracture, atrophic osteoarthritis, severe bone on bone osteoarthritis, knee pain attributable to disease other than osteoarthritis, or the subject has rapidly progressing osteoarthritis (RPOA) Type I or Type II.
12. The subject has significant malalignment of anatomical axis (medial angle formed by the femur and tibia) of the target knee (varus  $>10^\circ$ , valgus  $>10^\circ$ ) by X-ray as assessed by independent central readers at Screening Visit.
13. The subject has other conditions that could affect trial endpoint assessments of the index knee, including, but not limited to, rheumatoid arthritis, psoriatic arthritis, ankylosing spondylitis, gout or pseudogout, inflammatory bowel disease related arthropathy, peripheral neuropathy (e.g., diabetic neuropathy), lupus erythematosus, significant skin conditions overlying the index knee, acromegaly, metabolic joint diseases, and fibromyalgia.
14. The subject has significant pain in other areas, which may confound discrimination of pain assessment in the index knee.
15. The subject has evidence of cognitive impairment including dementia that may interfere with the subject's ability to complete patient reported outcomes (PROs).

16. The subject had systemic (except inhaled corticosteroid) immunosuppressant agent within 6 months prior to trial medication administration.
17. The subject has any surgery scheduled during the trial period.
18. The subject has current clinically significant disease(s) or condition(s) (including clinically significant cardiovascular disease) that may affect efficacy or safety assessments, or any other reason which, in the investigator's opinion, may preclude the subject's participation in the full duration of the trial.
19. The subject has a major bleeding disorder encompassing, but not limited to coagulopathy and any current antithrombotic and anticoagulant events.
20. The subject has a history of severe allergic or anaphylactic reactions.
  - The subject has history of hypersensitivity to local anesthetic (e.g., lidocaine, ropivacaine).
  - The subject has history of hypersensitivity to resiniferatoxin (RTX) or any similar component (capsaicin, chili peppers).
21. The subject has a known infection with human immunodeficiency virus or known current acute or chronic hepatitis B or C infection.
22. The subject has unstable or poorly controlled blood pressure which, in the opinion of the investigator, would put the subject at risk of severe adverse blood pressure increases upon IMP application.
23. The subject has evidence or history of severe psychiatric illness/disorder during the 3 years prior to the Screening Visit that, in the investigator's opinion, may affect efficacy or safety assessments or may compromise the subject's safety during trial participation (e.g., major depression, major anxiety disorder, psychosis, severe personality disorders).
24. The subject has a history of alcohol or drug abuse or was actively abusing drugs (including alcohol, medication) during the 1 year prior to the Screening Visit as judged by the investigator.
25. The subject has past or pending litigation due to chronic pain or disability.
26. The subject is known or suspected of not being able to comply with the requirements of the trial protocol or the instructions of the trial site staff.
27. The subject is not able to communicate meaningfully with the trial site staff.
28. The subject is currently participating or was participating in another investigational drug trial within 3 months prior to Screening visit.
29. The subject is an employee of the investigator or trial site, with direct involvement in the proposed trial or other trials under the direction of that investigator or trial site or is a family member of the employees or the investigator.
30. The subject has contraindications to an MRI of the index knee.
31. The subject has a history of malignancy within 2 years prior to the Screening Visit, with the exception of basal cell carcinoma.
32. The female subject is pregnant, planning on becoming pregnant, or is currently breastfeeding.

## 1.4 Trial treatments

### 1.4.1 Investigational medicinal products

The IMPs used in this trial are given below:

- 5 mL RTX-GRT7039 solution for intra-articular injection is constituted from 2 vials: 1 vial containing 1.6 µg/mL RTX supplied in 0.4 mL ethanolic solution and 1 vial containing 8 mL D- $\alpha$ -tocopherol polyethylene glycol succinate (TPGS) buffer.
- 5 mL placebo solution for intra-articular injection is constituted from 2 vials: 1 vial containing 0.4 mL ethanolic solution (placebo to match RTX-GRT7039) and 1 vial containing 8 mL TPGS buffer.

Details will be outlined in the pharmacy manual.

Five mL of IMP will be injected following ropivacaine administration (see Section 1.4.2), into the knee joint.

It is strongly recommended that the injection be assisted by ultrasound. Once completed, the needle and syringe will be removed, and an adhesive bandage applied.

The IMP injection will occur at the Randomization Visit (V2/Day 1).

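### Does the stated 400 ng dose contradict the vial strengths and volumes from which the injection is made up?

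*Combined protocol and SAP*

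**What the plan says.** Section 1.1 (Trial design) names the active arm as "RTX-GRT7039 400 ng single intra-articular injection".

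Section 1.4.1 (Investigational medicinal products) states that "5 mL RTX-GRT7039 solution for intra-articular injection is constituted from 2 vials". It then lists what each vial holds:

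- Active vial: "1 vial containing 1.6 µg/mL RTX", in a volume of 0.4 mL.
- Buffer vial: 8 mL.

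The two volumes stand together in the text as "RTX supplied in 0.4 mL ethanolic solution and 1 vial containing 8 mL" of buffer.

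The placebo is described in the same way, with a drug-free 0.4 mL vial. On administration the section says "Five mL of IMP will be injected following ropivacaine administration". On preparation it says only "Details will be outlined in the pharmacy manual". It gives no volume to be drawn from either vial, no mixed volume and no final concentration.

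**The concern.** A reader who sees a vial strength, two vial volumes and an injected volume will multiply them out. The natural first attempt is to add the two volumes, and that does not return 400 ng. The stated figure does appear if the 640 ng in the active vial is divided by 8 mL instead of 8.4 mL (640 / 8 x 5 = 400). This is what would result if someone had forgotten the 0.4 mL of active solution.

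If that were the explanation, the nominal dose would be wrong for the whole active arm, about 225 subjects according to Section 1.5.1. Each subject gets a single injection, so no later administration could correct it. The efficacy and safety results would then be attributed to a dose that nobody received.

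**Working it through.** **Inputs.** Stated dose 400 ng (Section 1.1). From Section 1.4.1: active vial 1.6 µg/mL = 1600 ng/mL, volume 0.4 mL; buffer vial 8 mL; injected volume 5 mL. Volumes are taken as additive and equal to the stated contents.

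**Formula.** Let v be the volume of active solution used (at most 0.4 mL) and b the volume of buffer used (at most 8 mL), with v + b at least 5 mL so that 5 mL can be injected. Then

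dose = 1600 x v / (v + b) x 5.

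**Step 1: the plan's own figure.** 400 ng in 5 mL is 80 ng/mL. From 1600 ng/mL this is a dilution of 1600 / 80 = 20-fold, so v + b = 20v, or b = 19v. The listed vials allow this over a range:

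- At the lower end the mixture is just 5 mL: v = 5 / 20 = 0.25 mL, b = 4.75 mL, dose = 1600 x 0.25 = 400 ng.
- At the upper end the whole active vial is used: v = 0.4 mL, b = 19 x 0.4 = 7.6 mL, mixture 8.0 mL, dose = 640 / 8.0 x 5 = 400 ng.

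Both ends, and everything between them, stay within 0.4 mL and 8 mL. The stated dose is reproduced exactly.

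**Step 2: the reading behind the concern.** With both vials used in full, v = 0.4 and b = 8:

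- active content 1600 x 0.4 = 640 ng
- mixture 0.4 + 8 = 8.4 mL, a dilution of 8.4 / 0.4 = 21-fold
- concentration 640 / 8.4 = 76.19 ng/mL
- dose 76.19 x 5 = 380.95 ng
- shortfall (400 - 380.95) / 400 = 4.8%

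This arithmetic is correct, but only for that choice of v and b.

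**Step 3: which reading does the text state?** Neither. Section 1.4.1 reports what the vials contain, not how much of each is used. Under any reading with 5 mL injected, 8.4 - 5 = 3.4 mL of the listed contents does not reach the subject, so vial content and amount used are different quantities. The product described as constituted is a 5 mL solution, which fits use of part of the contents at least as well as a full mix.

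**Step 4: is an omitted 0.4 mL shown?** No. A final volume of 8.0 mL results equally when the 0.4 mL is counted and 7.6 mL of buffer is used. The match with 640 / 8 x 5 cannot tell the two apart.

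These volumes only test whether the stated figures can agree. None is proposed as a preparation.

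**The case for a change.** The strongest reply is that every route to 400 ng needs a withdrawal volume that appears nowhere in the supplied text, and that the wording is open to more than one dose. Emptying both vials gives 381 ng. Making the whole active vial up to 5 mL would put all 640 ng into the injection, 60% above the stated dose. The reference to a 5 mL solution fits that reading too, so it does not by itself establish partial use. With one injection per subject, a preparation discrepancy could not be put right later.

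It is true that the dose cannot be derived from Section 1.4.1 alone. But a contradiction needs two statements that cannot both hold, and here 400 ng and the listed vials can. That several doses could be made from the same vials shows that the section is not a preparation instruction, and it does not claim to be one. The supplied text is a synopsis. Its page headings mark it as an extract from the final protocol, its footers count 78 pages, and a footnote to the schedule of events points to a Section 12.4.6 that is not included. Withdrawal volumes and final concentration belong in the pharmacy manual to which the section refers. Their absence from this extract is not evidence that they are absent or wrong in the plan.

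**Conclusion.** The concern does not hold. The 400 ng in Section 1.1 is consistent with the vial strength, vial volumes and injected volume in Section 1.4.1: a 20-fold dilution gives it exactly, within the listed contents. The figure of 381 ng, 4.8% lower, follows only if both vials are combined in full, which the documents do not state. No stated figure is shown to be miscalculated.

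This rests on additive volumes and on vial contents equal to those stated. It does not establish how the injection is actually prepared, because the pharmacy manual is not among the documents, and no view is taken on which dose or preparation is right. The sample size calculation in Section 1.5.1 does not use the dose as an input, so nothing in the statistical plan changes.

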### 1.4.2 Local anesthetic before IMP injection

Fifteen minutes prior to the intra-articular injection of IMP, a 5 mL intra-articular injection of ropivacaine 0.5% will be administered as a local anesthetic. Separate needles should be used for each, and the skin should be cleaned again prior to the administration of IMP.

Further details regarding the administration of ropivacaine are specified in a separate manual.

### 1.4.3 Prohibited and allowed medications or therapies

Subjects should not receive any of the following medications or therapies for the indicated times specified below:

- Intra-articular injection of corticosteroid or intra-articular visco-supplementation (i.e., hyaluronic acid) into the index knee within 90 days of screening and throughout the trial
- Injection of platelet-rich plasma or stem cells into the index knee within 6 months of screening and throughout the trial
- Topical capsaicin on the index knee within 3 months of screening and throughout the trial
- Any surgical intervention on the index knee (including but not limited to, arthroscopic interventions and knee replacement surgery) throughout the trial
- Any other investigational treatment or therapy

Subjects should continue their baseline non-pharmacological treatments and baseline analgesic and osteoarthritis medication(s) if the medications are not prohibited as outlined above, if they are on a stable, well-defined treatment regimen for at least 1 month before allocation to IMP and are anticipated to be able to maintain the treatment regimen in the opinion of the investigator.

There should be no changes (increases, decreases, or switches) from or additions to baseline analgesic medications (NSAIDs, opioids, other) and nonpharmacologic treatments after the Screening Visit through at least Week 26 (V6). This is designed to minimize possible confounding treatment effects due to alterations in pain medications.

Furthermore, subjects should not schedule any medical procedures, which would likely require an adjustment in pain medications during the trial and in particular for Weeks 10 to 12 and Weeks 24 to 26 if possible. Subjects not taking opioids at baseline should similarly refrain from starting opioid treatment.

If for any reason deemed necessary by the investigator, a subject requires additional medication(s) or change of dose, the medication(s), dosage change, route of administration, start and stop dates, and the indication for which it was given must be recorded in the source documents and a specific page in the eCRF.

All vaccinations, including coronavirus disease 2019 (COVID-19), are permitted during the trial.

